6. BIOSTATISTICAL ANALYSIS

6.1. Statistical analysis will be performed via a mixed model for repeated measures, with Drug (OXT vs. PLA) as a Class factor, psychometric scores as univariate and/or simultaneous multivariate dependent measures, additional covariates as appropriate, and Sbj as a random effect. Currently available mixed model analytic programs are able to handle missing data. Effect sizes will be employed in power analyses to calculate sample sizes for subsequent larger studies. Path analysis will be employed to test the role of bonding as a mediating factor of drug effect on depression outcome.

6.2. Power analysis. The major goal of this first study is to obtain measures of effect size that can be used to calculate sample size requirements for a subsequent, larger study, should the data from this study be promising. Thus, even if we are unable to meet the recruitment goals below, the study will still obtain useful and important data. That being said, we offer the following power analysis below, should recruitment go as well as hoped.

Because of the novelty of this project's hypothesis, no data are available regarding the potential protective effect of IN-OXT against the development of PPD, from which to estimate an effect size for the proposed study. However, a meta-analysis of studies of the effect of intranasal OXT in both healthy and clinical groups with implications for pharmacotherapy yielded an estimated effect size of $d=0.32$ (Bakermans-Kranenburg and van IJzendoorn, 2013), on which we will base our power analysis. With α set at 0.05, and $1-\beta$ (i.e., power) set at 0.80, $n=56$ Sbjs (approximately 28 completed Sbjs in each of two groups) will be required to detect an effect size of $d=0.32$ in a simple t-test analysis comparing OXT and PLA subjects. Estimating dropouts at 20% between assessments, 70 and 88 Sbjs and partners will have to complete the second and first postpartum assessments, respectively, and 110 Sbjs will be required to complete the pre-partum assessment. Of all pre-partum women given psychometrics, an estimated 20% will be found to be at-risk, requiring the administration of psychometrics to 550 study candidates. To summarize:

550 administered psychometrics

110 women identified at risk, pass final screening, and complete pre-partum assessment
88 women randomized, and complete assessment #2; 88 partners complete assessment #1 at day 1 postpartum

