NCT02505984

Preventing Postpartum Depression with Intranasal Oxytocin

Date of document: 12/27/2024

Data Analysis

The final sample size includes 38 eligible women randomly assigned to oxytocin administration ($n = 18$) or placebo ($n = 20$). Missing data were allowed such that 18.59% of the data were missing, with 23 different patterns. Jamshidian and Jalal's non-parametric Missing Completely At Random (MCAR) test indicated that the data was Missing At Random (MAR): Hawkins's test, $\chi^2_{\text{median}(6)} = 14.33$, $p_{\text{median}} = .026$, and Anderson-Darlin's rank test, $T_{\text{median}} = 5.88$, $p_{\text{median}} = .005$. Missing data was handled by Multiple Imputation (Rubin, 2009) with 50 complete sets. The reported basic results are the pooled outcome of the MI procedure. Before the primary analyses, we examined the normal distribution of all the quantitative study measures using a series of Anderson-Darling normality tests. Basic analyses for study group comparison on outcome measures for each time point were performed using Mann-Whitney U tests.

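### The SAP was written after the group comparisons, omits the protocol's mixed model and path analysis, and does not label its own tests as departures

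*SAP*

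**What the plan says.** Protocol section 6.1 gives the analysis in the future tense: "Statistical analysis will be performed via a mixed model for repeated measures, with Drug (OXT vs. PLA) as a Class factor", with the woman as a random effect. Missing data are left to that model: "Currently available mixed model analytic programs are able to handle missing data". A path analysis is to test whether bonding mediates the drug effect on depression. The specification is otherwise open: "psychometric scores as univariate and/or simultaneous multivariate dependent measures, additional covariates as appropriate". Section 2.1 names the hypothesised outcomes (bonding, depressive symptoms, PTSD symptoms) and two times (5 days and two months), with no single primary endpoint.

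The SAP is one section, Data Analysis, under the header "Date of document: 12/27/2024". It is in the past tense. It gives the final sample by arm (18 oxytocin, 20 placebo) and the missingness: "Missing data were allowed such that 18.59% of the data were missing, with 23 different patterns". It then gives statistics and p-values for a missingness test, says that its basic results are pooled over 50 imputed sets, reports that normality tests preceded the primary analyses, and closes with the comparison itself: "Basic analyses for study group comparison on outcome measures for each time point were performed using Mann-Whitney U tests".

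**The concern.** A statistical analysis plan is normally read as a statement of what was fixed before the outcome data were compared by arm. This one cannot serve that purpose, because its text already reports the comparisons as done. The one treatment comparison that the protocol does state in advance is not mentioned. A reader who has only the SAP would not learn that a repeated-measures model had been planned, or that imputation and separate rank tests at each visit were not in the protocol.

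Two things are at stake. First, when the planned and the described analyses differ without explanation, a reader cannot rule out selective reporting, even if none took place. Second, sections 6.1 and 6.2 of the protocol want effect sizes for sizing a later trial. Rank-test p-values at each visit do not directly supply them, whereas a fitted model with estimates and intervals does.

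**Working it through.** **1. Is the SAP retrospective?** It contains quantities that exist only after data collection: the arm sizes 18 + 20 = 38, the missing fraction of 18.59%, the 23 missingness patterns, and test statistics. One statistic can be checked. The SAP gives a median chi-square of 14.33 on 6 degrees of freedom with p = .026. The upper tail is P(χ²₆ > 14.33) = 0.0262, which matches. So this is a computed result and not a placeholder. The SAP also says that the group comparisons had been performed. The text therefore follows both the data and the comparisons.

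**2. Plan and SAP side by side.**

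| Item | Protocol 6.1 | SAP, Data Analysis |
|---|---|---|
| Treatment comparison | Mixed model for repeated measures, drug as factor, woman as random effect | Mann-Whitney U at each time point |
| Missing data | Left to the mixed model | Multiple imputation, 50 sets |
| Pre-tests | None | Missingness test; Anderson-Darling normality tests |
| Mediation | Path analysis | Not mentioned |
| Mixed model | Planned | Not mentioned |
| Primary analyses | Not a term used in 6.1 | Mentioned, not defined |
| Statement of departure | – | None |

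**3. How much could an unexplained choice matter?** The documents give no treatment p-values, so this is an illustration under stated assumptions.

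- Assumptions: no treatment effect; 18 vs 20 women; one outcome, normally distributed; complete data without imputation; correlation 0.5 between visits (the documents give none); two-sided 0.05 (the protocol's "With α set at 0.05" does not state sidedness).
- Test A: Mann-Whitney on the 2-month score.
- Test B: t-test on the mean of the day 5 and 2-month scores, standing in for the mixed model's average drug effect.
- Rejection rule for a free choice: min(p_A, p_B) < 0.05.

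With 20,000 null data sets, test A alone rejects 4.7% of the time. The smaller of the two p-values rejects 7.3% of the time, and 6.9% to 7.4% for correlations from 0.3 to 0.7. The simulation error on 7.3% is √(0.073 × 0.927 / 20,000) = 0.18 percentage points. A repeat with 200,000 data sets gave 4.8% for test A alone and 7.4% for the minimum at correlation 0.5 (7.7% at 0.3, 7.0% at 0.7).

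Each test used alone thus holds about 5%. The excess of about 2 percentage points arises only if both are run and the more favourable one is reported.

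**The case against.** The strongest reply is that the SAP hides nothing about its timing. It reports results openly, never calls itself pre-specified or confirmatory, and makes no efficacy claim. Protocol section 6.2 describes the study as a first one whose major goal is to obtain effect sizes. Section 6.1 is loose as well: outcomes may be univariate or multivariate and the covariates are open, so returning to it does not restore a single protected test. All of this stands. It limits the point to disclosure and order of reporting. It does not explain why the only model named in advance is missing, and section 2.1 does state a directional primary hypothesis that readers will want answered as planned.

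A reader might infer three stronger things, and the documents support none of them.

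- *That the mixed model was replaced.* The SAP speaks of basic analyses and, separately, of primary analyses, and never equates them. A mixed model may have been fitted and not described.
- *That the methods were chosen on the data.* Normality and missingness tests are reported ahead of the rank tests and the imputation, but the SAP does not say that they decided anything, and it gives no normality result. The past tense dates the text, not the decision. Neither document gives a database-lock or unblinding date, and an earlier SAP may exist.
- *That the reported tests have an inflated error rate.* A test written down late but used alone keeps its nominal rate. Inflation needs selection on results, which is not shown.

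**Conclusion.** The point holds as a failure to disclose and to carry through the planned analysis. Four facts can be read directly from the documents: the SAP postdates the data and the comparisons; multiple imputation and per-visit Mann-Whitney tests are not in the protocol; the section 6.1 mixed model and path analysis are not in the SAP; and the SAP leaves its primary analyses undefined and declares no departure. Why the methods differ, and whether the planned model was fitted, cannot be told from the documents.

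The consequence is that the Mann-Whitney results cannot be treated as pre-specified. The figure of about 7.3% against 5% is not an estimate of this trial's error rate. It shows what selective reporting between two analyses of one outcome could do, assuming complete normal data and a correlation of 0.5, with no allowance for the 18.59% missing or for imputation. The facts above do not depend on that figure.

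**What to change.** 1. State at the head of the SAP when it was written relative to data collection and the group comparisons. If an earlier dated SAP exists, cite it and say what changed.
2. Fit the section 6.1 mixed model and report it first, whatever it shows, for bonding, depressive symptoms and PTSD symptoms at day 5 and 2 months. Because 6.1 is open, write down the scale or scales used for each outcome, the time terms and one covariate set. Protocol sections 5.1.4 and 5.1.5 list two bonding scales at both visits (MIBS and PBQ); reporting both avoids a choice made after the fact. Give effect estimates with confidence intervals.
3. Define the primary analyses, and report the path analysis or say why it was not done.
4. Label the imputed Mann-Whitney results as not pre-specified and supportive, list imputation and the rank tests as departures with the reason for each, and make no confirmatory claim from them.

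The cost is a few model fits and some wording; no new data are needed. The downside is that the Mann-Whitney p-values become descriptive. The model's details will also be fixed after the data were seen, which the SAP should acknowledge.
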